#### 6.4. Covariates and Subgroups

All immunogenicity analyses will be conducted overall and stratified by baseline ZIKV seroprevalance for all Part A and Part B subjects. Additional summaries may be tabulated by clinical site, but the study is not powered for any additional subgroup analyses.

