# 6.3.2.1. Power Calculations for Evaluation of Safety

The goal of the safety evaluation for this study is to identify safety concerns associated with administration of the investigational vaccine. Two sample size calculations for safety are expressed in terms of two approaches, within group and comparing two groups.

The ability of the study to identify safety events may be expressed in terms of the probability of observing one or more event of interest (e.g., AEs) within each group assuming a range of underlying true event rates. With 1200 subjects per group and the true event rate of 0.3%, there is a probability of 97.3% to observe at least one event and a probability of 87.5% to observe more than one event (Table 6).

Safety event rates may vary considerably with the type of event considered. Safety will be evaluated within each arm and additionally stratified by baseline ZIKV status, pre-exposed or not.

•	•••	
True Event Rate (%)	Pr (0 event) (%)	Pr (more than one event) (%)
0.01	88.7	0.7
0.05	54.9	12.2
0.10	30.1	33.7
0.30	2.7	87.5
0.50	0.2	98.3

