# Table 6: Probability of Observing Safety Events within a Group (n=1200)

Table 7 provides the minimum detectable difference by two-sided chi-square test between the vaccine and placebo groups over a range of possible event rates and sample sizes as follows: 1200 samples per group, 960 samples per group to account for 20% early drop out, 480 and 240 samples per group for comparisons within a stratum defined by baseline ZIKV status.

Table 7:Minimum Detectable Difference in Event Rate Assuming Type I Two-Tail
Error Rate of 5%

Sample size	Event rate	Detectable wit	th 80% power	Detectable wi	th 90% power
group (#) (in placebo) (%)		Difference (%)	Event rate (in vaccine) (%)	Difference (%)	Event rate (in vaccine) (%)
	0.1	0.81	0.91	1.04	1.14
	0.5	1.19	1.69	1.46	1.96
1200	1.0	1.50	2.50	1.80	2.80
1200	5.0	2.80	7.80	3.29	8.29
	10.0	3.69	13.69	4.32	14.32
	25.0	5.11	30.11	5.93	30.93
	0.1	0.98	1.08	1.26	1.36
	0.5	1.39	1.89	1.71	2.21
960	1.0	1.73	2.73	2.09	3.09
	5.0	3.17	8.17	3.74	8.74
	10.0	4.16	14.16	4.88	14.88
	25.0	5.73	30.73	6.66	31.66
400	0.1	1.79	1.89	2.33	2.43
	0.5	2.30	2.80	2.88	3.38
	1.0	2.75	3.75	3.38	4.38
480	5.0	4.72	9.72	5.60	10.60
	10.0	6.08	16.08	7.15	17.15
	25.0	8.20	33.20	9.55	34.55
	0.1	3.38	3.48	4.43	4.53
	0.5	3.97	4.47	5.04	5.54
240	1.0	4.54	5.54	5.65	6.65
240	5.0	7.14	12.14	8.55	13.55
	10.0	8.98	18.98	10.61	20.61
	25.0	11.79	36.79	13.73	38.73

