# 6.4. Statistical Analysis

Study accrual is defined in this protocol as being randomized to a treatment group and receiving the first administration of study product. All accrued subjects will receive at least one product administration and therefore will provide some safety data. The safety population will include all enrolled subjects, summarized according to the actual vaccination dose received.

In **Part B**, all subjects will be tested for baseline ZIKV serostatus based on samples collected at Visit 02 prior to the first product administration. Since those with prior exposure to ZIKV may respond differently to the vaccine from those naïve subjects, safety, immunogenicity and efficacy will be analyzed within each stratum defined by baseline ZIKV status in addition to overall strata combined. **Part A** of the study is to be conducted at endemic or potentially endemic sites with baseline ZIKV serostatus tested, then safety and immunogenicity analyses will be similarly run by stratum in addition to overall strata combined.

Three types of analysis cohorts are defined. The Intent-to-treat (ITT) cohort will include all accrued subjects according to group assignment. The Per Protocol (PP) cohort will include all subjects receiving all planned vaccinations within window as assigned by the randomization schedule, and not experiencing any other major protocol deviations prior to the visit of

evaluation. The Modified intent-to-treat (mITT) analyses will include all accrued subjects who remain event-free one week after all planned product administration, where event is the primary efficacy event of a positive ZIKV PCR test result.

No multiple comparison adjustment will be employed for safety, immunogenicity, or efficacy analyses. Missing data will be primarily considered as missing completely at random in safety and immunogenicity analysis provided missing data is modest (e.g. <5-10%). For completeness, we will examine the missing data completely at random assumption and perform sensitivity analyses which weaken the missing completely at random assumption if the missing data is >10% or if the missing at random assumption is questionable. For efficacy, missing at random will be assumed and methods for handling missingness, such as multiple imputation and inverse propensity weighting, will be considered.

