In general, descriptive statistics by vaccine group will be tabulated for all variables of interest, stratified by baseline ZIKV testing results. This will include point estimates (mean, geometric mean, median or proportions) and their respective 95% CI or percentile spread. Formal comparisons will use standard methods, contingency tables for categorical variables, t-tests or non-parametric analogs for comparing means or geometric means, logistic regression and analysis of covariance for model discrete and continuous variables respectively.

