#### 8.3.1. Solicited Events and Symptoms

Solicited AEs will be recorded in the study database separately with data collection on the day of administration and for 7 days after each product administration, graded on a scale of 0 (none), 1 (mild), 2 (moderate) and 3 (severe), without the collection of attribution assessments. The solicited signs and symptoms on the diary card will include the following parameters: malaise (unusually tired/feeling unwell), myalgia (muscles aches (other than at injection sites), headache, chills, nausea, joint pain, and pain/tenderness at the injection sites. Subjects will also record the highest measured temperature per day and measurement per day of the largest diameter for redness and swelling at the injection sites, if applicable. Subjects are instructed to record the greatest local symptoms or measurement when evaluating multiple injection sites. Subjects will be provided with devices to measure temperature and diameter.

The number and percentage of subjects reporting at least one solicited event of any severity following any administration will be summarized for each solicited symptom, any systemic symptom, any local symptom, and any solicited symptom. The denominator is the number of subjects in the Safety Analysis Population with non-missing data for the symptom being summarized. The 95% CI along with p-values from a Chi-square test comparing treatment groups will be presented (Table 60 for **Part A** and Table 61 for **Part B**, **Appendix 1**). In cases where there is a small sample size (e.g. Part A), Fisher's exact 2-tailed test will be presented.

For each type of reactogenicity sign and symptom, the maximum severity (none, mild, moderate, severe, or missing) reported on Day 0 through Day 7 after each administration will be summarized. Similarly, the maximum severity across all systemic events and across all local events will be summarized. The number and percentage of subjects reporting each type of event, any systemic event, and any local event will be summarized by the maximum severity for each study group separately for each administration and over all administrations. (Table 62 for **Part A** and Table 63 for **Part B**, **Appendix 1**).

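### The protocol requires safety to be analysed by baseline ZIKV serostatus, but the SAP plans no serostatus split for solicited events, unsolicited AEs, the AE and SAE summaries or laboratory data

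*Combined protocol and SAP*

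**What the plan says.** The protocol makes the commitment more than once. Section 6.4 says of Part B that "safety, immunogenicity and efficacy will be analyzed within each stratum defined by baseline ZIKV status in addition to overall strata combined", because people with prior exposure may respond differently from naïve subjects. For Part A, where serostatus is tested, it adds "then safety and immunogenicity analyses will be similarly run by stratum in addition to overall strata combined". The same section sets a general rule: "descriptive statistics by vaccine group will be tabulated for all variables of interest, stratified by baseline ZIKV testing results". The safety power section, 6.3.2.1, repeats the point: "Safety will be evaluated within each arm and additionally stratified by baseline ZIKV status, pre-exposed or not". Table 7 then gives the "minimum detectable difference by two-sided chi-square test between the vaccine and placebo groups" for several sample sizes, including "480 and 240 samples per group for comparisons within a stratum defined by baseline ZIKV status".

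In the SAP, the subgroup section (6.4) reads "All immunogenicity analyses will be conducted overall and stratified by baseline ZIKV seroprevalance for all Part A and Part B subjects". Serostatus also appears in section 9 (neutralizing antibody), section 10 (efficacy) and section 8.4.3 with Table 107 (confirmed dengue). For solicited events, section 8.3.1 says "The 95% CI along with p-values from a Chi-square test comparing treatment groups will be presented"; the comparison is between study groups, without strata.

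These parts of the SAP show study group only:
- solicited events, Tables 60–63
- unsolicited AEs, Tables 64–96
- the overall AE summary, Table 97, and the SAE summary, Table 98
- laboratory tables 110–166, and the laboratory GEE models, whose covariates are group, time and their interaction

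Sections 8.4.1 and 8.4.2 say that the listings of deaths, SAEs and new chronic conditions will carry each subject's baseline serostatus. The shells for Tables 99 and 100 (SAEs) and 104 (new chronic conditions, the template for 105) show no such column.

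**The concern.** Safety is a primary objective in both parts. The protocol gives a reason for looking at pre-exposed subjects separately and shows what differences the within-stratum comparison could detect. The SAP's preface says it describes every analysis the data center will conduct, so an analysis missing from both its text and its shells is not planned.

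If the SAP is followed as written, no table gives a by-arm rate within a serostatus stratum for reactogenicity, unsolicited AEs, SAEs or laboratory abnormalities. An excess limited to one stratum would be averaged over the whole arm, and a pooled test could easily miss it.

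**Working it through.** **Inputs.** Protocol Table 7: 1200, 960, 480 and 240 per group; placebo rates of 0.1% to 25%; two-sided chi-square test at 5%; detectable differences at 80% and 90% power.

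**Formula.** With n per group, placebo rate p0, vaccine rate p1 and mean rate p̄:
- SE0 = √[2·p̄(1−p̄)/n]
- SE1 = √{[p0(1−p0) + p1(1−p1)]/n}
- power = Φ[(p1 − p0 − 1.96·SE0)/SE1]

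**Step 1: reproduce Table 7.** Solving for the difference gives 45 of the 48 entries to two decimals; the other three differ by 0.01. For n = 240 and 5.0% against 12.14%: p̄ = 0.0857, SE0 = 0.02555, SE1 = 0.02534, so power = Φ[(0.0714 − 0.0501)/0.02534] = Φ(0.84) = 80%.

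**Step 2: dilute the same excess.** Table 7 does not say what its strata are fractions of. Assume 240 and 480 out of 1200, so f = 0.20 or 0.40, and no excess in the other stratum. The pooled vaccine rate is f × (stratum rate) + (1 − f) × p0.

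For f = 0.20 and p0 = 5%: 0.20 × 12.14 + 0.80 × 5.0 = 6.43%. The difference is 1.43 points, against the 2.80 that Table 7 gives as detectable with 1200 per group. With n = 1200, SE0 = 0.00948 and SE1 = 0.00947, so power = Φ[(0.01428 − 0.01857)/0.00947] = Φ(−0.45) = 33%.

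**Step 3: run all placebo rates.** In every row the stratum vaccine rate is the one Table 7 gives for 80% power.

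| Placebo rate (%) | 240: stratum rate (%) | 240: pooled rate (%) | 240: pooled power | 480: stratum rate (%) | 480: pooled rate (%) | 480: pooled power |
|---|---|---|---|---|---|---|
| 0.1 | 3.48 | 0.78 | 71% | 1.89 | 0.82 | 74% |
| 0.5 | 4.47 | 1.29 | 54% | 2.80 | 1.42 | 64% |
| 1.0 | 5.54 | 1.91 | 46% | 3.75 | 2.10 | 59% |
| 5.0 | 12.14 | 6.43 | 33% | 9.72 | 6.89 | 50% |
| 10.0 | 18.98 | 11.80 | 29% | 16.08 | 12.43 | 47% |
| 25.0 | 36.79 | 27.36 | 26% | 33.20 | 28.28 | 44% |

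**Step 4: change the base.** If the strata are taken from Table 7's 960 per group (25% and 50%), pooled power runs from 31% to 73% and from 53% to 76%.

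**The case against.** Several points on the other side stand.

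- **Pooled tables are not blind.** A reader might infer that the planned tables cannot show a risk confined to pre-exposed subjects. The documents do not support that. Pooling lowers power, and at a 0.1% placebo rate the loss is small (71% and 74% against 80%).
- **SAEs are partly covered.** The SAP text puts serostatus in the SAE listing. Protocol 1.4 reports six SAEs among 1058 Part B subjects by July 24, 2018, and with so few a listing showing arm and serostatus could reveal clustering. What remains is that the shells omit the column, listings give no denominators, and the SAE summary (Table 98) has no split.
- **SAP 6.4 is not exclusive.** A reader might take its sentence as limiting serostatus analyses to immunogenicity. It does not say so, and the SAP stratifies efficacy and dengue elsewhere. The protocol's own safety section, 6.4.2, does not mention strata either. The defect is a protocol commitment left unimplemented.
- **A single power figure would mislead.** The result depends on stratum share, placebo rate and the assumption of no excess in the other stratum. If that stratum carried half the excess in the 5% example, the pooled rate would be 5 + 0.20 × 7.14 + 0.80 × 3.57 = 9.28%, and pooled power about 98%.
- **The SAP carries some warnings.** Section 8.6 cautions against reading a non-significant laboratory comparison as no difference.
- **Nothing is lost for good.** Serostatus is a stored baseline variable, so the tables could be produced later.

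Two possible defences do not hold. SAP 2.1 says that not all protocol analyses are detailed, but the class it names as left out is exploratory endpoints. SAP 6.4 says the study is not powered for additional subgroups, but Table 7 gives detectable differences for exactly these strata.

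**Conclusion.** The protocol and SAP conflict. The protocol requires safety by baseline ZIKV serostatus in Part B, and similarly in Part A. The SAP delivers this for dengue only and gives no reason for omitting it for solicited events, unsolicited AEs, the AE and SAE summaries and laboratory data. Its text and shells also disagree on whether the SAE and new-chronic-condition listings show serostatus.

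The cost is loss of sensitivity. Where the stratified comparison has 80% power, the pooled one has about 26% to 71% (240 of 1200) or 44% to 74% (480 of 1200) over Table 7's placebo rates; at 5% it has about 33% and 50%. These figures assume an excess in one stratum only. The true seropositive share is not given; planning Table 11 uses 0% to 30%. This is a gap in planned reporting that should be closed; it does not affect the design or data collection.

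**What to change.** - **SAP 6.4:** add safety to the analyses done overall and by baseline ZIKV serostatus, or state and justify the departure from the protocol.
- **Part B tables:** add ZIKV-negative and ZIKV-positive rows, laid out as in Table 107, to the solicited, unsolicited AE, overall summary, SAE summary and laboratory distribution tables. Give the arm difference with a 95% CI in each stratum.
- **Part A:** show the strata descriptively only, since there are 30 subjects per group before any split.
- **Missing serostatus:** SAP 6.3 expects some subjects without a result. Count them in the overall rows only.
- **Shells:** add the serostatus column to Tables 99, 100, 104 and 105 so that they match sections 8.4.1 and 8.4.2.
- **Baseline sample:** protocol 6.4 takes serostatus from Visit 02 and SAP 3.2.1 from Visit 01. Reconcile these, since the result defines the new rows.

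The cost is SAP wording and table programming; no new data are needed. The downside is a longer report with small strata and, under protocol 6.4, no multiplicity adjustment, so the stratum results must be read descriptively.

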#### 6.5. Missing Data

Missing data will be primarily considered as missing completely at random in safety and immunogenicity analyses provided missing data is modest (e.g. <10%). For completeness, we will examine the missing data completely at random assumption and perform sensitivity analyses which weaken the missing completely at random assumption if the missing data is >10% or if the missing at random assumption is questionable. Data will be presented as available; no imputation is planned. For efficacy, missing at random will be assumed and imputation may be implemented if supported by the data and if sufficient consequence to justify their inclusion.

#### 6.6. Interim Analyses and Data Monitoring

#### 6.6.1. Independent Safety Reviews

The Protocol Safety Review Team (PSRT) will review safety data routinely throughout the study. The study will utilize both electronic database features and reviews by designated safety review personnel to identify in a timely manner if any of the safety pause rules of the study are met. The NIAID Data and Safety Monitoring Board (DSMB) will provide an independent safety review at scheduled intervals to coincide with their biannual meeting schedule.

#### 6.6.2. Immunogenicity Reviews:

**Part A:** The data in Part A will be used in an ongoing manner to help select the regimen to be used in Part B. Analyses will be performed as described in Section 9.

**Part B:** An interim analysis of immunogenicity data may be performed after the NAb assays up to and including Week 12 have been completed on a subset of subjects. Analyses will be performed as described in Section 9. Reports will be provided to the Protocol Chairs and other key investigators as described in the study blinding plan solely for the purpose of informing future trial-related decisions in a timely manner. Results will be provided summarized by treatment arm, and to prevent inadvertent unblinding, no individual subject data will be released that would indicate study group. The results will remain confidential and should in no way influence the conduct of the VRC 705 trial in terms of early termination or later safety or immunogenicity endpoint assessments.

#### 6.6.3. Incidence Reviews (Part B only):

The study will be regularly monitored using the combined (blinded) incidence rates for ZIKV disease and for ZIKV infections. These rates will be monitored at each site and over all sites combined. Such monitoring will allow for enrollment to be expanded or curtailed at different sites.

Prior to completion of enrollment of the 2400 Part B subjects, calculations using the blinded incidence rates will be performed to estimate the expected time to achieve 90 cases of ZIKV disease. Based on these calculations, the sample size may remain fixed at 2400, be increased up to 15,000, or the trial may be stopped for lack of feasibility if this expected time is deemed excessive.

#### 6.7. Multicenter Studies

Data will be pooled across all clinical sites. Center effects are not anticipated because the sites are using standardized procedures for study product administration and assessment of solicited and unsolicited AEs, and the study relies on central laboratories for the assessment of immunogenicity and clinical efficacy endpoints.

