# 6.3.2. Sample Size Considerations: Part B

**Part B** of the study targets healthy adults and adolescents ages 15 to 35 years who reside in ZIKV endemic or potential endemic regions. This age range is considered to be the range of the highest reproductive potential and therefore, this age group will likely be the initial target for a successful ZIKV vaccine. Additionally, the risk of GBS has been shown to increase with age, so

this study population excludes those who might be at higher perceived risk for GBS [54-56]. Randomization at each study site will equally allocate subjects to vaccine or placebo schedules. The randomization plan does not include provisions for replacing subjects with incomplete product administration or visit schedules.

A total of 2400 subjects will be randomized 1:1 to receive either the study vaccine or placebo. The study sample size was determined primarily based on the evaluation of vaccine efficacy (VE). The study also has ample sample size for detecting AEs, therefore meeting the primary endpoints.

To detect a VE of 61%, the trial aims to achieve 90 cases of naturally acquired virologic ZIKV infection within 2 to 3 years. If it appears this target is unlikely to be met, the study may be expanded to achieve this target. Prior to the completion of randomization, the combined vaccine and placebo incidence rate of subclinical ZIKV cases will be calculated. At each site, the blinded site-specific baseline seropositivity rate may be calculated and used to adjust the needed sample size and to aid in allocation of enrollment slots. Both types of rates will be used to help decide if the enrollment should be extended to allow for the target to be achieved. For planning purposes, we will allow for a total sample size of up to 15,000. Such a sample size could achieve our target number of virologic ZIKV cases within 3 years, assuming full accrual within 12 months, even if the placebo incidence rate is as low as 0.50% and the seropositive rate is as high as 30% among enrollees.

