# 6.4.4. Analysis of ZIKV Incidence

Efficacy evaluation with respect to ZIKV incidence will be performed in **Part B**. Incidence rates for ZIKV cases will be described by vaccine group and by baseline ZIKV stratum for each group. Results will be treated both as dichotomous (infection, no infection) and as a time to event (infection) variables. The primary analysis will be based on the time to case of virologic ZIKV infection, i.e., when a subject is positive for ZIKV based on a PCR test. The time to ZIKV case data, accounting for censoring, will be described using Kaplan-Meier curves and efficacy computed using a Cox proportional hazards model. VE will be estimated by the hazard ratio from the Cox proportional hazards model stratified by baseline ZIKV exposure status.

The primary efficacy analysis is a test of the null hypothesis (H0): the study vaccine has VE no more than 20% in preventing ZIKV infection, i.e., VE  $\leq$  20%, where ZIKV infection is defined as virologically confirmed infection by PCR virus detection. The alternative hypothesis is that VE > 20%. The criterion for success will be that a one-sided test of H0 has p-value  $\leq$  0.025. This primary analysis will be based on the mITT cohort stratified by baseline serostatus (prior exposed to ZIKV or not). If the null VE  $\leq$  20% is not rejected, an additional test of H0\*: VE = 0 will be conducted using a one-sided type I error rate of 0.025.

The secondary efficacy analyses include the testing of this hypothesis over the two stratum combined. Another secondary analysis will test the above hypothesis H0, where ZIKV infection is defined as PCR virus detection irrespective of symptoms. The SAP will provide any necessary additional specificity and/or cohort definitions such as discussed at the beginning of Section 6.4.

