#### Incidence Reviews (Part B only):

The study will be regularly monitored using the combined (blinded) incidence rates for ZIKV disease and for ZIKV infections. These rates will be monitored at each site and over all sites combined. Such monitoring will allow for enrollment to be expanded or curtailed at different sites.

The trial will periodically evaluate the expected time to achieve 90 cases of virologic ZIKV disease and may be stopped for lack of feasibility if this expected time is deemed excessive.

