# 6.4.6. Randomization of Treatment Assignments and Unblinding Criteria

Randomizations will be done online using an electronic randomization system. The randomization code will be prepared by the Protocol Statistician and included in the enrollment module for the trial. The randomization code will link to the treatment assignment. The electronic data system will assign each subject a randomization code after eligibility has been confirmed in the system.

In **Part A**, randomization will be performed with 1:1:1 allocation to the three vaccination arms at each study site. In **Part B**, randomization will be performed with 1:1 allocation to the ZIKV DNA vaccine and placebo at each study site.

**Part A** will be open-label and no unblinding will be needed. In **Part B**, the injections will be prepared by an unblinded site pharmacist, designee, or otherwise qualified personnel who will not be involved in any subject assessments and who will not discuss randomizations with blinded study staff. The subjects, the study personnel who perform product administrations and

assessments, data entry personnel at the sites, and laboratory personnel performing immunologic assays will be blinded to the treatment assignment of all product administrations. Product assignments will be provided to the site PI at completion of the study per the Study Blinding Plan for communication to the study subjects. The DSMB may receive data in aggregate and presented by treatment group, but without the treatment group identified. The DSMB may be unblinded to individual study treatment assignments, as needed, to adequately assess safety issues.

The IND Sponsor intends to unblind treatment assignments for **Part B** of the study once 90 cases of ZIKV infection are detected. The DSMB will be consulted prior to unblinding.

If necessary, the site PI or designee and Protocol Chair may agree that an event, such as management of an AE or pregnancy, requires emergency unblinding of an individual subject's assignment. If early unblinding occurs for any reason, it will be documented as a protocol deviation. The Protocol Statistician, the site IRB/EC (as required), and the DSMB will be notified that an early unblinding has occurred and provided with a statement explaining the medical necessity for the early unblinding.

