#### **10.2.** Analysis of vaccine efficacy:

The time of ZIKV events is defined as the illness onset date recorded on the ZIKV Endpoints eCRF (for clinical cases) or date first specimen was collected with a positive PCR or other Zika result, whichever is earliest. Time to event for analysis will be as follows:

- For subjects with infection: time of ZIKV event minus date of first administration (Visit 02) + 1.
- For subjects with no infection: date of protocol completion/termination as recorded on the study status eCRF minus date of first administration (Visit 02) + 1. These subjects will be censored at their date of study completion or date of early termination.
- Subjects with or without infection may be censored from the analysis for the PP population as described in Section 6.3.

For subjects who were randomized but did not receive any product, date of randomization will be used in place of date of first administration in the definitions above.

The cumulative incidence of ZIKV cases will be presented graphically as 1 – Kaplan-Meier curves. Curves will be presented by study group and baseline ZIKV stratum and by study group combined over all subjects (Figure 27 through Figure 44, Appendix 2). Similar presentations will be displayed for virologic ZIKV cases and subclinical ZIKV cases).

Vaccine efficacy will be estimated as 1 - Hazard Ratio estimated from a Cox proportional hazard model. The primary efficacy analysis for ZIKV infection will use the following test:

H0: VE 
$$\leq 20\%$$
  
H1: VE  $\geq 20\%$ 

The criterion for success will be that a one-sided test of  $H_0$  has p-value  $\leq 0.025$ . Success will be met if the lower bound of the 95.0% confidence interval for VE estimated for the mITT population using a Cox proportional hazards model stratified by baseline ZIKV status is >20 (Table 51 through Table 53, Appendix 1).

If the null hypothesis VE  $\leq 20\%$  is not rejected, then the following will be tested using a one-sided type I error rate of 0.025.

H\*0: VE =0% H\*1: VE >0%

As secondary analyses of vaccine efficacy this hypothesis will be tested for:

- ZIKV cases without stratification for baseline ZIKV serostatus
- virologic ZIKV cases stratified by baseline ZIKV serostatus
- subclinical ZIKV cases stratified by baseline ZIKV serostatus
- subclinical ZIKV cases without stratification for baseline ZIKV serostatus

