#### **10.2.1.** Sample SAS code for time to event analysis:

Notations

Timevar = the variable that gives the time to occurrence Censorvar = the variable indicating whether timevar is censored, where 1 = censored, 0 = not censored (event) Trtmnt = study product (placebo or ZIKVwt DNA) Stratavar = variable indicating baseline ZIKV serostatus

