#### Cox Proportional Hazard

SAS Code for stratified Cox Regression [4] to obtain Vaccine Efficacy and 95% CI for Vaccine Efficacy:

```
Proc phreg;
CLASS trtmnt (ref = 'placebo') / param = ref;
STRATA stratavar;
MODEL timevar*censorvar(1)=trtmnt (and any covariates)/rl;
ODS OUTPUT ParameterEstimates=ests (keep=HazardRatio HRUpperCL
HRLowerCL);
RUN;
```

Calculate the following from the estimates obtained from the PROC PHREG output:

Vaccine Efficacy = 1 – HazardRatio Lower 95% CI= 1 – HRUpperCL Upper 95% CI= 1 – HRLowerCL

Similar code will be used to fit the cox regression combined across ZIKV serostatus stratum by removing the STRATA statement on PROC PHREG.

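### Part B is randomised within site, but the primary Cox model leaves site out, for a reason that does not cover differences in Zika transmission; the cost is a modest loss of power

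*Combined protocol and SAP*

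**What the plan says.** **Randomisation.** Protocol 6.4.6 states that in Part B "randomization will be performed with 1:1 allocation to the ZIKV DNA vaccine and placebo at each study site". Protocol 6.3.2 agrees: "Randomization at each study site will equally allocate subjects to vaccine or placebo schedules". Site is the only randomisation factor named.

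**Primary model.** Protocol 6.4.4: "VE will be estimated by the hazard ratio from the Cox proportional hazards model stratified by baseline ZIKV exposure status". SAP 10.2 sets the success criterion on the lower confidence limit for VE in the mITT population, "using a Cox proportional hazards model stratified by baseline ZIKV status is >20". The sample code in SAP 10.2.1 defines its stratum as "Stratavar = variable indicating baseline ZIKV serostatus", and its model line is "MODEL timevar*censorvar(1)=trtmnt (and any covariates)/rl", which names no site term.

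**Reason for pooling sites.** SAP 6.7: "Center effects are not anticipated because the sites are using standardized procedures for study product administration". It goes on to cite standardised assessment of adverse events and central laboratories for the immunogenicity and efficacy endpoints.

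**What the plan expects of the sites.** Protocol section 4 assigns Part B slots partly on local epidemiology and lets them move with the epidemic. Protocol 6.3.2 allows each site's baseline seropositivity to inform sample size and slots. On blinded incidence by site, protocol 6.4.5 says: "Such monitoring will allow for enrollment to be expanded or curtailed at different sites". SAP 6.6.3 repeats this.

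**Site in the efficacy output.** Site appears only in descriptive incidence tables (SAP 10.1, Tables 48 to 50). No site-stratified efficacy analysis is specified, even as a sensitivity analysis.

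**The concern.** The endpoint is infection, and its main driver is how much Zika circulates locally. Standardised injections and a central PCR laboratory make measurement comparable; they do not make exposure comparable. The argument in SAP 6.7 therefore cannot be reconciled, for efficacy, with the sections that manage enrolment on the expectation of site-to-site differences in transmission.

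Leaving out a strong prognostic factor matters in a Cox model even when the arms are balanced on it. At high-transmission sites, placebo subjects become cases and leave the risk set faster than vaccinated subjects. In the pooled risk set, the vaccine arm gradually comes to hold relatively more high-exposure subjects, and the hazard ratio drifts towards 1. Because success requires the VE lower limit to clear 20%, that drift costs power. The analysis also omits the one factor on which the randomisation was balanced.

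**Working it through.** **1. The plan's own figure.** Inputs from protocol 6.3.2.3: 90 cases, VE 61%, null VE 20%, one-sided alpha 0.025, and vaccine share of cases (1−VE)/(2−VE).

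- Null share p0 = 0.80/1.80 = 0.4444. Alternative share p1 = 0.39/1.39 = 0.2806.
- SE under the null = √(0.4444 × 0.5556/90) = 0.0524. SE under the alternative = √(0.2806 × 0.7194/90) = 0.0474.
- z = (0.1639 − 1.96 × 0.0524)/0.0474 = 1.29, so power is 90.2%.

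A logit version also gives 90.2%, with 66 and 90 cases for 80% and 90% power (Table 9 prints 66 and 89). The exact binomial gives 89.0%. The stated 90% reproduces.

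**2. Simulation of pooled against site-stratified analysis.** From the documents: 2400 subjects, 1:1 within site, true VE 61%, placebo incidence of about 3% a year, about 2 years. Success means that the upper 95% Wald limit for the hazard ratio is below 0.80. Assumed, because the documents do not give them: number of sites, site sizes and the CV of site incidence. Monte Carlo error is about 0.5 to 1 point.

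| CV of site incidence | Sites | Power, pooled | Power, stratified by site |
|---|---|---|---|
| 0 | 20 | 88.6% | 88.7% |
| 0 | 30 | 88.8% | 88.8–88.9% |
| 1 | 10 | 88.2% | 89.1% |
| 1 | 20 | 87.2% | 88.2% |
| 1 | 30 | 87.3% | 88.3% |
| 2 | 10 | 83.5% | 87.0% |
| 2 | 20 | 82.4% | 87.3% |
| 2 | 30 | 82.2% | 86.8% |

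The comparison to make is across each row. Down the table, both columns also fall because mean events drop from about 88 to about 82.

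**3. Where the loss comes from.** With 20 sites and CV 2, the mean log hazard ratio is −0.9045 pooled and −0.9529 stratified, with standard errors of 0.2452 and 0.2455. Stratification costs no precision. The estimate moves by 0.9529 − 0.9045 = 0.0484, about 0.2 of a standard error. Median VE at CV 2 is about 59% pooled and about 61% stratified.

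**4. Type I error.** With true VE 20% and CV 2, rejection is 1.5–1.6% pooled and 2.2–2.3% stratified, against a nominal 2.5%. Neither analysis is inflated.

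**5. Against the planned model itself.** Step 2 has no serostatus strata. A separate run compared serostatus only with serostatus by site, assuming mean seropositivity of 30% varying by site and a seropositive hazard one-tenth of the seronegative hazard. Events were not fixed at 90, so only the differences matter.

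- CV 2: power 73.9% v 78.2% (17 sites) and 76.5% v 81.4% (30 sites), gains of 4.3 and 4.9 points.
- CV 1: gains of 0.4 to 1.2 points.
- CV 0: 0.4 points lower with site, within Monte Carlo error.
- About 25 cases: 34.6% v 34.3% at CV 1, and 28.8% v 30.5% at CV 2. Finer strata do not harm the model when cases are few.

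**6. The expanded design.** Protocol 6.3.2 allows up to 15,000 subjects at 0.5% placebo incidence with 30% seropositive, which leaves 0.70 × 15,000 = 10,500 at risk. With 20 sites, 3 years and about 90 events, power is 89.3% v 89.5% at CV 1 and 87.8% v 88.5% at CV 2, a gain of at most 0.7 points. Depletion of high-risk subjects is slight when cumulative incidence is this low.

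**The case against.** The strongest reply is that the pooled analysis is sound and the loss is small wherever the assumptions are realistic. Much of that stands.

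- **Validity.** A reader might infer that site confounds the vaccine comparison, or that the pooled test could produce a false claim. The documents do not support this: allocation is 1:1 within every site, and the pooled test errs against the vaccine.
- **Size.** CV 2 is extreme. Under a gamma distribution over 17 sites, the median site has about 0.17 of the mean incidence, 44% of sites have under a tenth of it, and two sites carry about 58% of the total site rate. Nothing in the documents supports such a spread, and moving slots towards active sites works against it. A separate 17-site run gave 89.3% v 89.7% at CV 0.5 and 87.5% v 88.5% at CV 1.
- **Estimand.** A hazard ratio averaged over sites is a legitimate target, and the plan's power calculation is itself pooled. The shift from 61% to 59% is therefore a gap between two quantities as much as an error in one.
- **Site is not ignored.** It is monitored and tabulated, and the sample code leaves room for covariates. But an unnamed covariate is not a pre-specified site term, and descriptive tables do not enter the success criterion.

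The reply does not rescue the stated reason. SAP 6.7 is apt for safety and assay data, but it says nothing about transmission. Nor does it show any material cost of including site.

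**Conclusion.** The mismatch is real: randomisation is by site, the model is by serostatus alone, and the reason for pooling does not address exposure. It is a matter of efficiency and of matching analysis to design, not of validity. With 2400 subjects and 10 to 30 sites, the loss is nil at CV 0, about 1 point at CV 1 and about 3.5 to 5 points at CV 2; in the 15,000-subject design it is about 1 point or less. A reader might take 5 points as the expected loss; it belongs only to the extreme assumed spread. The number of sites and the CV are assumptions throughout. Dropout, interim looks and the mITT exclusion were not modelled and should affect both analyses alike. Since stratifying by site showed no material loss of power and no inflation in any setting, the change is worth making.

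**What to change.** Before unblinding:

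- Stratify the primary Cox model by serostatus and site. Fix, on blinded data, a rule for pooling sites with few cases, for example by country or region.
- Keep the serostatus-only model as a sensitivity analysis.
- Align protocol 6.4.4, SAP 10.2, the definitions and code in SAP 10.2.1, and the log-rank p-values in SAP Tables 54 to 56.
- In the secondary models without serostatus strata, drop serostatus but keep site. The SAP's instruction to remove the whole STRATA statement would remove site as well.
- Limit the SAP 6.7 rationale to procedures, adverse event assessment and assays.

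The cost is more than one line of code. Protocol 6.4.4 lets the SAP add detail, but it names serostatus as the stratum, so both documents, the table specifications and the pooling rule need work. No new data are needed. Sites without cases contribute nothing to the stratified likelihood, which loses almost no information.
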